STUDY PROTOCOL PLAN AND STADISTICAL ANALYSIS PLAN (SAP)

UNIVERSITY CEU CARDENAL HERRERA

Principal investigator: [name] [name]

TITLE: Textural Analysis and Effect of ROI Size on Infrared Thermography in Athletes With Patellar Tendinopathy. A Cross-sectional Study

Research and Ethics Committee of University Católica San Antonio, Number: CE111803

NCT ID:

DATE: 07-23-2025

STUDY PROTOCOL PLAN

Objectives:

The objectives of our study have been the following:

The objectives of this study were: (1) to evaluate differences in thermal and GLCM-based textural features between athletes with PT and healthy controls; (2) to compare the diagnostic performance of IT and GLCM features applied to thermographic images; and (3) to identify the most appropriate ROI size for optimal characterization of PT using both thermal and textural analysis.

Volunteers who want to participate in the study will read the general information of the study and sign the informed consent to participate in the study.

Once the informed consent has been read and delivered, the evaluator will check that they meet the inclusion criteria.

Participants will be divided into two groups: (1) athletes with unilateral PT, diagnosed using a combination of clinical criteria, specific functional tests, and ultrasound evaluation. Additional inclusion criteria for this group included a symptom duration of more than 3 months, a VISA-P score of less than 80, and a differential diagnosis to rule out other possible causes of anterior knee pain; (2) healthy volunteer athletes, recruited under the inclusion criteria of no previous history of PT and a VISA-P score of 100.

Participants with any other lower limb pathology, nerve or vascular disorder, or skin lesion in the knee area that could alter the thermal information of the patellar tendon region will be excluded from both groups.

All participants were instructed not to engage in physical exercise; not to drink alcohol, coffee or energy drinks 12 hours before the measurements; not to smoke in the previous 6 hours; not to apply creams or lotions to their legs to avoid altering skin emissivity; to report any medication or treatments they were taking; and to try to avoid altering their rest and meal habits. These requirements minimise the influence of individual extrinsic factors on the IT results.

Recorded variables

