The data will be analysed using IBM SPSS Statistics for Windows v.25.0 (IBM Company, 2017). The normality and homoscedasticity of the variables will be checked. The data will be summarised using absolute and relative frequencies for categorical variables, and means \pm standard deviations (SD) and 95% confidence intervals for continuous variables.

Independent sample t-tests will be used to compare continuous variables, and a chi-square test will be used to compare categorical variables at baseline between PT patients and controls.

One-way analysis of covariance will be used to analyse the thermal difference and textural characteristics between PT patients and healthy controls, controlling for the effects of clinical and demographic covariates. Cohen's d statistic will be calculated to assess the effect size (d > 0.1 small, around 0.3 medium, and >0.5 large).

To calculate the diagnostic accuracy of the thermal difference and textural characteristics based on first- and second-order statistical analysis, simple logistic regression will be performed for age, sex, and BMI by group, including them in subsequent models if $p < 0.20$. Sensitivity (Se), specificity (Sp) and Youden's index (expressed as $Se + Sp - 1$) will be investigated, as well as the positive and negative likelihood ratios (LRp and LRn) of thermal difference, textural characteristics and their combinations. The thermal difference and textural characteristics will be introduced one by one and in all possible combinations (255 models) in the logistic regression analyses, including a maximum combination model containing all characteristics.

Receiver operating characteristic (ROC) curves will be used and the Hosmer-Lemeshow goodness-of-fit test will be performed by comparing the observed and expected frequencies of the outcome variable ($p > 0.05$ indicates a good fit). The Brier score will be calculated to evaluate the accuracy of the probabilistic predictions, where lower scores indicate better model performance. An area under the curve (AUC) value close to 90% and sensitivity and specificity values above 80% are considered acceptable.

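### The multi-feature diagnostic models are judged on the participants used to fit them, with no internal validation, so AUC, sensitivity, specificity and Brier score will tend to look too good against the plan's acceptability rule

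*Combined protocol and SAP*

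**What the plan says.** All of this is in the Statistical Analysis Plan (SAP) section unless noted.

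- **Models.** The predictors are the thermal difference and "textural characteristics based on first- and second-order statistical analysis". They are to be "introduced one by one and in all possible combinations (255 models) in the logistic regression analyses", "including a maximum combination model containing all characteristics".
- **Covariates.** Before that, "simple logistic regression will be performed for age, sex, and BMI by group, including them in subsequent models" when p < 0.20.
- **Measures.** Se, Sp, Youden's index and both likelihood ratios are reported for the features and their combinations, together with ROC curves, a Hosmer-Lemeshow test and a Brier score, "where lower scores indicate better model performance".
- **Rule.** An AUC near 90% is wanted, and "sensitivity and specificity values above 80% are considered acceptable".
- **Objectives** (Study Protocol Plan). Objective 2 is "to compare the diagnostic performance of IT and GLCM features applied to thermographic images". Objective 3 is "to identify the most appropriate ROI size for optimal characterization of PT using both thermal and textural analysis".

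The document describes one set of participants, athletes with patellar tendinopathy and healthy controls. It mentions no split sample, cross-validation, bootstrap, shrinkage or external sample. It does not say in words that accuracy is computed on the fitting data, but it describes no other data.

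**The concern.** A logistic model fitted by maximum likelihood adapts to chance patterns in its own data. With many coefficients and few cases, accuracy measured on those data is on average better than the same fitted model would achieve in new athletes. The gap grows with the number of coefficients and shrinks with N.

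The plan then holds these figures to a numerical standard. A multi-feature model could be called acceptable although its accuracy in new athletes would fall short. The checks that the plan names give no protection, because Hosmer-Lemeshow and Brier on the fitting data reward the same overfitting.

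**Working it through.** **1. The plan's own count.** All non-empty subsets of k features number 2^k − 1. This gives 127 for k = 7, 255 for k = 8 and 511 for k = 9, so 255 means eight features. Eight models have one feature and 255 − 8 = 247 have several. With zero to three covariates the largest model has 8 to 11 slopes.

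**2. Implied N.** The section on determination of sample size gives OR = 5, α = 0.05, power 0.80, R² = 0.1 and a binary predictor with proportion 0.5. It gives no N, sidedness or baseline probability P0. The usual formula for a binary predictor with B = 0.5 is

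N = [z_α·√(P̄(1−P̄)/B) + z_β·√(P0(1−P0) + P1(1−P1)(1−B)/B)]² / [(P0−P1)²(1−B)(1−R²)].

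For example, take a two-sided test and an assumed P0 = 0.3. The odds are 5 × 0.3/0.7 = 2.143, so P1 = 0.682 and P̄ = 0.491. The numerator is (1.96 × 0.707 + 0.8416 × 0.653)² = 3.746. The denominator is 0.1458 × 0.5 × 0.9 = 0.0656. N is 57.1, rounded up to 58.

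With P0 from 0.1 to 0.6 and the common variants of the formula, N is 57–105 two-sided and 45–83 one-sided. With equal groups that is (45/2)/11 ≈ 2 to (105/2)/8 ≈ 6.6 cases per slope in the largest model.

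**3. Optimism of the planned all-feature model.** This case needs no model selection and no optimised cut-off. Assumed, because the documents give none of it: equal groups, normal features, a common correlation ρ and no covariates. Each setting used at least 600 simulated data sets. Apparent means on the fitting data; true means the same fitted model in the population. The achievable AUC is Φ(D/√2). With one differing feature, D² = d²(1+6ρ)/[(1−ρ)(1+7ρ)], which for d = 0.8 gives 0.714, 0.775 and about 0.88 at ρ = 0, 0.5 and 0.8. With eight equal features, D² = 8d²/(1+7ρ), and d = 1.36 at ρ = 0.5 gives 0.90.

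| Setting | N = 60, apparent vs true | N = 100, apparent vs true |
|---|---|---|
| One feature, d = 0.8, ρ = 0: AUC | 0.79 vs 0.65 | 0.76 vs 0.67 |
| Same, ρ = 0.5: AUC | 0.83 vs 0.72 | 0.81 vs 0.74 |
| Same, ρ = 0.8: AUC | 0.92 vs 0.84 | 0.90 vs 0.86 |
| Achievable AUC 0.90, ρ = 0.5: AUC | 0.93 vs 0.86 | 0.92 vs 0.88 |
| Same: Se and Sp at cut-off 0.5 | 0.86 vs 0.78 | 0.84 vs 0.80 |

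In the last row the apparent values clear 80%. The true values are below it at N = 60 and about at it at N = 100.

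**4. Single-feature models.** A pre-specified feature with d = 0.8 and no covariates shows almost no AUC optimism (0.715 vs 0.714 at N = 70). The plan, however, also screens covariates for these models. With three noise covariates screened at p < 0.20, AUC is 0.74 vs 0.70 at N = 60 and 0.73 vs 0.70 at N = 100. A Youden cut-off chosen in the same data raises Se and Sp by about 0.05 each at N = 70.

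**5. Choosing the best of the 255.** At ρ = 0.5 with one feature differing and N = 60, the model with the highest apparent AUC shows 0.838 vs 0.721. The all-feature model shows 0.834 vs 0.720 on the same basis. Selection adds a little; most of the bias is already there.

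**6. Objectives 2 and 3.** Suppose the thermal set is real, the texture set is pure noise, and apparent AUC decides. At N = 60 texture then wins in 38% of data sets with 1 thermal and 7 texture features, but in 2% with 4 and 4. For two ROIs with one real feature each (d = 1.0 and 0.6), the apparent AUC gap is 0.085 against a true 0.129 at N = 60, and 0.092 against 0.127 at N = 100.

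**The case against.** The strongest reply is that the amounts are the reviewer's and not the plan's. N, signal and correlation are all unstated, and the table shows how far the results move with correlation alone. That stands: the figures are illustrations with a range and do not predict this study's results. It does not touch the direction, which was the same in every multi-feature setting tried.

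Second, the plan states no rule for picking a best model or a cut-off, so rates built on the best of 255 models or on a Youden cut-off rest on steps it does not commit to. That also stands, and the main case here therefore uses only the all-feature model at a fixed cut-off.

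Third, the rule can be read as a descriptive benchmark in a cross-sectional study, with no stated decision behind it and no numerical bound on how near to 90% the AUC must be. This is fair as to consequences. A stated threshold will still be read as a performance claim, and the values set against it are biased in its favour.

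Three stronger readings are tempting and are not supported:

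- **That the analysis is rigged towards texture.** The document does not say which models answer objective 2 or how the eight features divide. It does not say on which side first-order statistics fall. A tilt arises only if multi-feature models are used and the two sets differ in size.
- **That one ROI size is favoured.** If the same eight features are used for each ROI, neither gains; at most a real difference shrinks.
- **That poor models will usually pass.** With one feature differing at correlation 0.5 and N = 60, the all-feature model's mean apparent values (AUC 0.83, Se and Sp about 0.75) do not meet the rule.

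**Conclusion.** The plan is wrong as written on this point. It applies an acceptability rule to same-data accuracy from models with up to 8 to 11 slopes and has no step to remove the optimism.

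For the all-feature model the AUC excess in the settings tried is 0.07 to 0.14 at N = 60 and 0.04 to 0.09 at N = 100. Se and Sp are too high by about 0.08 and 0.04 at those sizes when an AUC of 0.90 is achievable, which is where a favourable conclusion is most plausible. These amounts rest on equal groups, normal features and the assumed signals and correlations; the direction does not.

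A reader might infer that the single-feature models are safe. They are less affected but not exempt, because of the covariate screen and any cut-off chosen in the same data.

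**What to change.** Add to the SAP:

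1. Internal validation of the whole procedure, by repeated cross-validation or an optimism bootstrap. The covariate screen, any model selection and any cut-off choice are redone in each resample.
2. Validated AUC, Se, Sp, Youden's index and Brier score with 95% confidence intervals, reported beside the apparent values.
3. A statement that the acceptability rule, and any IT-versus-GLCM or ROI comparison of multi-feature models, uses the validated values and their intervals.
4. A statement that in-sample Hosmer-Lemeshow and Brier results are not evidence against overfitting.

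Comparing one thermal and one texture model of equal size removes only the set-size tilt, so it does not replace validation.

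**Does it work?** Five repeats of 5-fold cross-validation were tried on the best of 255 models, with three noise covariates screened and one real feature at correlation 0.5. Apparent, true and cross-validated AUC were 0.847, 0.714 and 0.698 at N = 60, and 0.817, 0.736 and 0.724 at N = 100. A bootstrap on the eight-feature model at N = 70 moved AUC from 0.84 to 0.76 (true 0.75) with moderate signal, and from 0.68 to 0.55 (true 0.50) with none. Some optimism therefore remains with the bootstrap.

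Point estimates alone are not enough. With achievable AUC 0.90, cross-validated estimates (with AUC of at least 0.875 taken as near 90%) still met the rule in 14% (N = 60) and 16% (N = 100) of data sets, against 0% and 1% truly meeting it.

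**Cost.** No new participants or data. If all 255 models are run, five repeats of 5-fold cross-validation are 25 × 255 = 6,375 fits per ROI, and 500 bootstrap resamples are 500 × 255 = 127,500. Scripting is needed, probably outside SPSS v25. Reported accuracy will be lower and noisier. The intervals are approximate: a simple version covered the true AUC in 88–92% of data sets with signal and 79% without.

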Demographic and clinical characteristics (gender, age, BMI, and duration of evolution) will be recorded. The severity of patellar tendinopathy will be measured using the widely accepted and valid Victorian Institute of Sport Assessment-Patella (VISA-P) questionnaire. All thermal image recordings were performed by the same researcher.

Determination of sample size

The sample size will be calculated using G*Power v.3.1.9.7 software (Heinrich-Heine University) for a logistic regression design to evaluate the diagnostic accuracy of IT in distinguishing between patients with PT and healthy controls, taking into account the possible inclusion of covariates. The parameters are set as follows: odds ratio = 5, alpha error probability $\alpha = 0.05$, power $1-\beta = 0.80$, R^2 for other covariates = 0.1, binomial distribution with a proportion $\pi = 0.5$.

Image acquisition protocol

TI images will be recorded with an OPTRIS PI 450 IRT camera coupled to Optris PI Connect software (Germany). The IRT camera has a noise equivalent temperature difference <40 mK with a field of view of $38^\circ \times 29^\circ$, a wide temperature range of -20 °C to $+100$ °C, a spectral range of $7.5-13$ μ m, a focal plane array sensor size of 382×288 pixels, an emissivity set to 0.98, and a measurement uncertainty of $\pm 2\%$ of the global temperature reading. The capture frame size was 55.4×40.63 cm (1.5 mm/px).

The participant will acclimatise in an isolated room (3.86×3.47 m²), without temperature sources, at an average temperature of (23.7 ± 0.9 °C) and relative humidity of ($49 \pm 5\%$) for 15 minutes without clothing on the lower extremities. The participant will sit on a hydraulic stretcher with their feet on a step to isolate contact with the floor, and the camera will be positioned perpendicular to the subjects for a more accurate reading. Two rectangular ROIs will be selected on each knee using a previously described method by superimposing ROIs on thermal images using markers on the skin. a) an ROI of the patellar tendon (tendon ROI); b) an ROI of the anterior part of the knee (knee ROI) using the anatomical references of the upper pole of the patella, anterior tibial tuberosity, and lateral contour of the knee.

Statistical Analysis Plan (SAP)

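### Models with up to eight features plus covariates are planned as plain logistic regression with no penalty or separation rule; at the size the plan's inputs imply, this worsens probability predictions and, at strong signal, risks separated fits

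*Combined protocol and SAP*

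**What the plan says.** In the Statistical Analysis Plan, the paragraph on diagnostic accuracy has the thermal difference and the textural features "introduced one by one and in all possible combinations (255 models) in the logistic regression analyses". The same sentence then describes the largest of these models: "including a maximum combination model containing all characteristics". For covariates, "simple logistic regression will be performed for age, sex, and BMI by group, including them in subsequent models if" their p-value is below 0.20. On software, "The data will be analysed using IBM SPSS Statistics for Windows v.25.0". The plan names no penalised, Firth or exact method, no action for separation or non-convergence, and no internal validation. Models are judged by AUC, sensitivity, specificity, Youden's index, likelihood ratios, the Hosmer-Lemeshow test and the Brier score. The target is an AUC near 0.90 with sensitivity and specificity above 0.80.

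Under Determination of sample size, the calculation is "for a logistic regression design to evaluate the diagnostic accuracy of IT in distinguishing between patients with PT and healthy controls", allowing for covariates. "The parameters are set as follows: odds ratio = 5", with alpha 0.05, power 0.80, R² 0.1 and a binomial predictor with proportion 0.5. The section gives no resulting N, no sidedness and no baseline probability.

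**The concern.** The study is sized for one predictor adjusted for covariates, and the same participants then support models with 8 to 11 coefficients. The textural features come from the same images and are probably correlated. With so few cases per coefficient, maximum likelihood tends to overstate coefficients and give predicted probabilities that are too extreme for new patients. If a combination of features splits the two groups perfectly, no finite estimate exists. The program can then still print AUC = 1, sensitivity and specificity of 100%, an unbounded positive likelihood ratio and a Brier score near zero. Such a fit would meet every accuracy target in the plan.

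Two things are at stake. One is the Brier score, which the plan itself chose for judging probability predictions. The other is the risk that a failed fit is presented as a perfect classifier. Validating afterwards would expose poor probabilities but not improve them, and separated resamples would disturb a bootstrap.

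**Working it through.** **Number of features.** Non-empty subsets of k features number 2^k − 1. For k = 8 this is 255, which reproduces the plan's count. The largest model therefore has 8 coefficients, or up to 11 with age, sex and BMI.

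**Implied sample size (an assumption, since no N is stated).** Inputs from the sample-size section: OR 5, so β = ln 5 and β² = 2.590; proportion 0.5; R² = 0.1; alpha 0.05; power 0.80. Assumed: a two-sided test, so z-values 1.960 and 0.842, and a baseline probability p0. With p1 = 5p0/(1 + 4p0) and V = 2/[p0(1 − p0)] + 2/[p1(1 − p1)]:

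- Wald form: N = (1.960 + 0.842)² V / [β²(1 − R²)].
- With null variance: N = (1.960√V0 + 0.842√V)² / [β²(1 − R²)], where V0 = 4/[p̄(1 − p̄)] and p̄ = (p0 + p1)/2.

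| p0 | p1 | V | V0 | Wald N | Null-variance N |
|---|---|---|---|---|---|
| 0.309 (half are cases) | 0.691 | 18.73 | 16.0 | 63.1 → 64 | 56.6 → 57 |
| 0.5 | 0.833 | 22.4 | 18.0 | 75.4 → 76 | 64.9 → 65 |

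The two-sided range is thus about 57 to 76. One-sided, with p0 from 0.2 to 0.5, it is 45 to 60. Over all variants tried (p0 from 0.1 to 0.6) it is 45 to 105.

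**Cases per coefficient, equal groups.** 29/11 = 2.6 at the low end; 38/8 = 4.8 at the high end.

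**Simulation design.** Two equal groups; eight normally distributed features, correlated 0.5 where performance on new patients was measured; 0 or 3 further predictors. Separation was detected by linear programming (400 data sets per cell). Performance was measured on 4,000 new participants. The ridge penalty was chosen by cross-validation.

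**Prediction at N = 58, true AUC 0.90.**

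| Predictors | New-patient Brier, ML | Ridge | New-patient AUC, ML | Ridge |
|---|---|---|---|---|
| 8 | 0.165 | 0.151 | 0.861 | 0.871 |
| 11 | 0.190 | 0.158 | 0.836 | 0.857 |

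An uninformative prediction scores 0.25. At true AUC 0.80 with 11 predictors, Brier was 0.234 against 0.215, while AUC was 0.734 against 0.728, slightly lower with ridge. A separate set of runs gave ridge the better mean Brier score in every scenario. Its mean AUC change ranged from −0.035 to +0.03, with the clearest loss at weak signal (N = 64, correlation 0.8, true AUC 0.75: 0.644 with ridge against 0.679).

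**Separation, maximum model (8 / 11 predictors).**

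| N | True AUC 0.90 | True AUC 0.95 |
|---|---|---|
| 46 | 11% / 32% | 41% / 69% |
| 58 | 1.5% / 10% | 18% / 41% |
| 76 | 0.3% / 1% | 4.5% / 16% |

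Repeat runs put the N = 58 figures at AUC 0.95 at about 20% to 45%. Monte Carlo error is modest: for 10%, √(0.1 × 0.9/400) = 1.5 percentage points. At N = 58 with 11 predictors, separation was 0% at true AUC 0.80 and 3% at 0.87.

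**Same-sample figures (N = 58, 11 predictors, true AUC 0.90).** Apparent AUC was 0.948 with maximum likelihood and 0.940 with ridge, against 0.836 and 0.857 on new patients. The optimism is 0.948 − 0.836 = 0.112 and 0.940 − 0.857 = 0.083. For Brier, ridge roughly halves the optimism, from 0.108 to 0.055.

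**Do combinations appear to win?** With only one informative feature (N = 58, 8 features plus 3 covariates), the full model beat that feature on same-sample AUC in 100% of data sets under maximum likelihood and 86% to 88% under ridge. On new patients it never did.

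**The case against.** The strongest objection is that the estimator is the lesser problem. A reader might infer that plain maximum likelihood is what would distort the verdict on combinations, and that a penalty would cure it. The 100% against 86% to 88% result does not support that: the distortion comes mainly from judging 255 models on the data that fitted them. Nor do finite estimates make a separated sample honest. In separated samples at N = 58, mean same-sample AUC was still 0.995 to 0.998 with Firth and 0.989 to 0.997 with ridge. This objection stands, and it is why the fix must include internal validation.

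The risk is also easy to overstate. Eleven predictors is the upper limit: if age, sex and BMI are independent and unrelated to group, all three enter with probability 0.2³ = 0.8%, and none or one enters with probability 0.8³ + 3 × 0.2 × 0.8² = 90%. Real imbalance would raise the number entering. The largest separation figures need a true AUC of 0.95, above the plan's own target. This also stands.

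A third tempting reading is that maximum likelihood always discriminates worse. The AUC results contradict it; the consistent loss is in probability predictions.

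Finally, neither N nor maximum likelihood is stated. The first is handled by a range. The second is the natural reading of unqualified logistic regression in SPSS; if a penalised fit was meant, the SAP needs to say so.

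**Conclusion.** The concern holds in a limited form. As written, the SAP fits up to 8 features and 3 covariates with no penalty and no rule for separation, at about 2.6 to 4.8 cases per coefficient if N is 57 to 76. At N = 58 and true AUC 0.90, this costs 0.165 − 0.151 = 0.014 (8 predictors) to 0.190 − 0.158 = 0.032 (11 predictors) in new-patient Brier score. The AUC cost is about 0.01 to 0.02 at true AUC 0.90, and nil or slightly reversed at 0.80. Separation is about 1% to 10% at 0.90, about 20% to 45% at 0.95, and near zero at 0.80.

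These sizes rest on assumptions that the documents do not supply: N, normal features, their correlation, equal groups and the true AUC. A smaller study would fare worse and a larger one better. The documents do not support describing separation as likely in general, or the estimator as the main reason combinations would look superior.

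**What to change.** Amend the diagnostic accuracy paragraph of the SAP before analysis:

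1. State the estimator. Fit every model with more than one feature by ridge logistic regression on standardised features, with the penalty chosen by cross-validation.
2. Check each model for separation, report where it occurs, and do not present AUC = 1 or sensitivity and specificity of 100% from a separated fit as accuracy estimates.
3. Compare single-feature and combination models on internally validated performance, by bootstrap or cross-validation that repeats the penalty choice and the model selection in each resample. Do not base the comparison on the fitting data. This also puts models fitted by different estimators on a common footing.
4. State the planned N, the sidedness and the baseline probability, so that cases per coefficient can be read from the plan.

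No new data are needed. The costs are a routine probably outside the SPSS menus, odds ratios from combination models that are shrunken and less readable, and slightly less favourable reported accuracy.

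### A non-significant Hosmer-Lemeshow test is read as good fit, but it shows only that no misfit was detected, and run on the fitting data it cannot reveal overfitting

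*Combined protocol and SAP*

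**What the plan says.** The last paragraph of the SAP section plans ROC curves and says that "the Hosmer-Lemeshow goodness-of-fit test will be performed by comparing the observed and expected frequencies of the outcome variable"; in brackets it adds that p > 0.05 "indicates a good fit". The number of groups is not given.

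The rule applies to a large set of models. The thermal and textural features enter singly and "in all possible combinations (255 models) in the logistic regression analyses", up to a model holding all of them. Age, sex and BMI are added where they reach p < 0.20.

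The same paragraph plans a Brier score, with lower values better, and calls an AUC near 90% with sensitivity and specificity above 80% acceptable. It describes no calibration slope, intercept or plot, and no bootstrap, cross-validation or test on other data.

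On size, the section on determination of sample size says "The sample size will be calculated using G*Power v.3.1.9.7 software" and lists inputs, but gives no resulting N, baseline probability or sidedness.

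**The concern.** There are two separate problems.

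1. **Power.** The test takes perfect fit as its null hypothesis. Failing to reject is informative only if the test would probably have rejected had the fit been poor. With a few participants in each risk group, that cannot be assumed.
2. **In-sample testing.** As described, the test uses the data that produced the coefficients. A model that has chased noise agrees with those data by construction, so the test does not address overfitting. Yet overfitting is the main calibration threat when eight features plus covariates are fitted to a small sample.

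A model could therefore be reported as fitting well on the strength of a result that gives little such support. That would colour the comparison of diagnostic performance in the second objective.

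**Working it through.** **No plan figure to reproduce.** The documents state neither N nor the power of the fit test, so N was bracketed first and the pass rate then simulated.

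**Step 1: number of features.** 2^8 - 1 = 255, so there are eight features.

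**Step 2: implied N.** Inputs from the sample-size section: odds ratio 5, alpha 0.05, power 0.80, "R^2 for other covariates = 0.1", binary predictor with B = 0.5. Assumed: sidedness, and baseline p1 = P(Y=1|X=0).

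With p2 = 5·p1/(1 - p1 + 5·p1) and P = (p1 + p2)/2:

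N = [z_alpha·√(P(1-P)/B) + z_beta·√(p1(1-p1) + p2(1-p2)(1-B)/B)]² / [(p1 - p2)²(1-B)] ÷ (1 - R²)

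Balanced outcome, two-sided: p1 = 0.309, p2 = 0.691, P = 0.5. This gives 51.4 before the covariate adjustment, and 51.4/0.9 = 57.1, so N = 58.

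The Wald variant is N = (z_alpha + z_beta)²·[1/((1-B)p1(1-p1)) + 1/(B·p2(1-p2))]/(ln 5)² ÷ (1 - R²). It gives 56.8/0.9 = 63.1, so N = 64.

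| Sidedness | Baseline 0.2-0.5 (Wald) | Baseline 0.1 (Wald) |
|---|---|---|
| Two-sided | 58-68 (64-76) | 91 (105) |
| One-sided | 45-53 (50-60) | 71 (83) |

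With ten groups, N = 58 means 58/10 = 5.8 participants per group.

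**Step 3: pass rate under misfit.** The statistic is the sum over groups of (O - E)²/[E(1 - E/n)], referred to chi-square with 8 df. A straight-line logit in one standard normal predictor x was fitted to data with a different true logit, with 4000 runs per cell. Entries are the percentage with p > 0.05.

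| True logit | N=46 | N=58 | N=76 | N=104 |
|---|---|---|---|---|
| Mild curvature: ln5·x + 0.25(x²-1) | 95 | 94 | 94 | 94 |
| Moderate curvature: ln5·x + 0.5(x²-1) | 93 | 91 | 89 | 86 |
| Moderate U: 0.5(x²-1) | 86 | 80 | 75 | 63 |
| Threshold: 2 if x>0.8, else -0.7 | 84 | 77 | 67 | 53 |
| Step: 1.5 if x>0, else -1.5 | 76 | 68 | 58 | 42 |
| Strong curvature: ln5·x + (x²-1) | 73 | 64 | 49 | 35 |
| Strong U: x²-1 | 59 | 45 | 26 | 11 |

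Correctly specified models pass about 95-96%. An omitted interaction passed 86% (moderate) and 62% (strong) at N = 60. A separate simulation at N = 50/58/76 gave 89/89/83% for moderate curvature and 74/72/55% for a step; the ranges in the verdict span both.

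**Step 4: pass rate under pure noise.** Eight noise features were fitted to balanced groups.

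| N | Pass, fitting data | Apparent AUC | AUC, new data | RMS error of fitted probability | Pass, new data |
|---|---|---|---|---|---|
| 46 | 96% | 0.74 | 0.50 | 0.21 | 28% |
| 58 | 95% | 0.71 | 0.51 | 0.18 | 35% |
| 76 | 96% | 0.68 | 0.50 | 0.16 | 43% |
| 104 | 94% | 0.65 | 0.50 | 0.14 | 47% |
| 1000 | 95% | 0.55 | 0.50 | 0.04 | 63% |

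Fitting all 255 subsets of eight noise features at N = 58, an average of 242 passed. This is what the 5% level predicts: 255 - 0.05 × 255 = 242.25.

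**The case against.** The strongest reply is that the test is one item among several and decides nothing. The only results called acceptable are an AUC near 90% with sensitivity and specificity above 80%, and nothing says that Hosmer-Lemeshow selects a model. Noise models would rarely meet that bar. With AUC of at least 0.85 taken as near 90% and the best in-sample cut-off, eight noise features met it in 1.3% of 2000 runs at N = 46, 0.2% at N = 58 and none at N = 76. With three added covariates the rates were 5.1% at N = 46 and 0.7% at N = 58. This stands: a reader might infer that the rule certifies the chosen model, but the documents do not give it that role. It does not rescue the rule, because the AUC, Brier score, sensitivity and specificity are also in-sample as described, and none is corrected for optimism.

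A reader might also take the noise pass rate as a small-sample failure. It is not. It is the nominal 95% at every N tried, including 1000, because a model of noise features is not wrong in form. Small size matters here only because overfitting is larger (RMS error 0.18 at N = 58 against 0.04 at N = 1000).

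It is also fair to say that calibration is secondary to the stated objectives and that no risk-prediction tool is planned. That limits the severity.

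**Conclusion.** The point holds as a wrong inference rule of minor-to-moderate weight. At about 46 to 76 participants the test passes most mild-to-moderate misfit: moderate curvature about 83-93%, a step effect about 55-76%. At any N, it passes about 95% of models made only of noise.

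Two stronger readings are not supported. One is that the test passes misfit in general: a strong U-shape passes 45% at N = 58 and 26% at N = 76, and power is better near N = 100. The other is that the plan treats the test as proof: the text says only that the result indicates fit.

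The misfit figures rest on an N inferred from the stated inputs, on ten groups, and on simulated shapes that the documents do not specify. If the baseline probability is 0.1, N is 71 to 105 and the power problem is smaller. The overfitting conclusion does not depend on N.

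**What to change.** In the SAP's ROC paragraph, replace the bracketed rule with a statement that p > 0.05 means no misfit was detected. State the number of groups and keep the test as descriptive only.

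For the reported model or models, give bootstrap optimism-corrected calibration slope and intercept with confidence intervals, and a smoothed calibration plot. If one model is chosen from the 255, repeat that selection within each bootstrap sample; otherwise the correction leaves out the optimism due to choosing.

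No new data are needed. The cost is modest extra analysis, possibly outside base SPSS.
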